8. BENEFIT-RISK EVALUATION

Pharmacological and efficacy studies with Rifaximin (see Investigator's Brochure) have shown that the benefits of Rifaximin include:

- The negligible absorption of Rifaximin (less than 1%) means it has an excellent safety profile and can be administered at high doses for long period time.
- No potential for either inhibition or induction of human hepatic cytochrome P450 at expected clinical plasma concentrations.
- No drug-drug interactions with oral contraceptives at expected clinical plasma concentrations.
- Rifaximin can be administered with or without food.
- A large antimicrobial spectrum covering most gram-positive and -negative bacteria, including aerobes and anaerobes and therefore good activity against the microflora normally present in both the small intestine and in the colon.
- Rifaximin is widely used in gastroenterology (i.e. Traveller's diarrhoea, Hepatic Encephalopathy and Irritable Bowel Syndrome with diarrhoea IBS-D).
- Bioavailability studies with Rifaximin-EIR 1200 mg (3 x 400 mg tablet) administered TID for 7 days showed that absorption is negligible in subjects with Crohn's Disease (CD). Absorption is negligible also in subjects with IBS receiving Rifaximin 550 mg TID for 14 days.
- Rifaximin works by decreasing the triggers of immune activation as well as enteric inflammatory response, rifaximin may reduce the uncontrolled immune response to enteric bacteria.
- Based on the available evidence summarized in a recent meta-analysis on 32 clinical trials through March 2015, Rifaximin is effective and safe in eradicating SIBO and resolving symptoms (overall success with an intention-to-treat: 70.8%) (Gatta, 2017). According to Gatta and colleagues, SIBO eradication rates increase linearly with increasing Rifaximin dose, in the 600to-1600 mg daily dose range. With regards to safety data, in the above-mentioned meta-analysis the 4.6% of SIBO patients treated with Rifaximin reported AEs, but only the 0.47% of them had to discontinue the therapy.
- Data from randomized clinical studies, evaluating the efficacy of Rifaximin 200 mg TID (1200 md/day) in rosacea patient's positive for SIBO, demonstrated that eradication of SIBO induced an almost complete regression of cutaneous lesions among patients achieving glucose breath test negativity after treatment (Parodi, 2008) (Weinstock, 2013).

The safety of Rifaximin evaluated in clinical trial and during post-marketing surveillance indicates that Rifaximin is extremely safe. In details:

- The safety of Rifaximin-EIR has been evaluated in 6 studies, 3 Phase II studies involving 379 patients with mild to moderate Crohn's disease, 1 PK study on 18 healthy volunteers and 2 PK studies on 30 patients with active Crohn's disease. The safety analysis has shown a favourable safety profile of Rifaximin-EIR in the treatment of mild to moderate active Crohn's disease.
- The safety of Rifaximin (200 mg or 550 mg formulations) has been extensively established in approximately 7000 subjects enrolled in clinical studies (IBS-D: 4020 subjects; Hepatic Encephalopathy: 697; Traveller's Diarrhoea: 1527; healthy volunteers: 221) and of Rifaximin 600 – 1800 mg in approximately 125 patients (receiving rifaximin 1100 mg/day for 2 years),
- Post-marketing experience confirmed that Rifaximin is extremely safe.

Overall, in clinical trials (including those investigating Rifaximin-EIR), nearly all adverse reactions recorded were uncommon (<1%). The most frequently reported adverse events were related to

gastrointestinal, nervous, skin and general disorders, in addition to those revealed by laboratory findings.

The incidence of adverse events in people treated with rifaximin was comparable to or lower than that in the placebo-treated patients, as one would be expected from a non-absorbable antibiotic. In some of the cases, gastrointestinal adverse events recorded during clinical studies were also symptoms of the intestinal disease to be treated with the investigational drug.

In addition to those identified during clinical trials, further potential risks may include:

- Cases of *Clostridium Difficile* Associated Diarrhoea (CDAD) have been reported with Rifaximin use, ranging in severity from mild diarrhoea to fatal colitis. The potential association of Rifaximin treatment with CDAD and Pseudomembranous Colitis (PMC) cannot be ruled out.
- Allergic reactions have also been reported during post-approval use. Systemic absorption of Rifaximin is approximately 0.4% of the orally administered dose; however, even these very low quantities are sufficient to trigger an allergic reaction, particularly in hypersensitive subjects. Therefore, serious unpredictable reactions such as anaphylactic shock or severe skin reactions may occur.
- Cases of both increases and decreases in International Normalised Ratio (INR) with a temporal association with Rifaximin administration were reported in patients maintained on warfarin and Rifaximin with a temporal association with rifaximin administration. Therefore, closer INR monitoring and/or dose adjustment of warfarin is required around the time of Rifaximin administration.
- In healthy subjects, clinical drug interaction studies demonstrated that rifaximin did not significantly affect the pharmacokinetics of CYP3A4 substrates, however, in hepatic impaired patients it cannot be excluded that Rifaximin may decrease the exposure of concomitant CYP3A4 substrates administered (e.g. antiepileptics, antiarrhythmics), due to the higher systemic exposure with respect to healthy subjects.
- In healthy subjects, co-administration of a single dose of cyclosporine (600 mg), a potent Pglycoprotein inhibitor, with a single dose of Rifaximin (550 mg) resulted in 83-fold and 124-fold increases in Rifaximin mean C_{max} and AUC∞. The clinical significance of this increase in systemic exposure is unknown.
- There is no experience regarding administration of Rifaximin to subjects affected by an undiagnosed systemic bacterial infection potentially treatable with rifampicin.

Experts have agreed that the systemic absorption of Rifaximin is too low to select resistant strains, and in fact, two recent surveys carried out in Italy, where Rifaximin has been widely used since 1987, found no evidence of development of resistance by *M. tuberculosis* or *N. meningitides*. Therefore, the clinically relevant selection of cross-resistant *M. tuberculosis* or *N. meningitides* is considered not probable.

In summary, the properties of Rifaximin, including its broad range of activity against bacteria, the supposed immunomodulatory activity, its low systemic availability, the excellent safety profile, the clinical efficacy shown in Proof of Concept studies in the treatment of rosacea, support a positive risk/benefit ratio.

9. SELECTION OF STUDY POPULATION

9.1 Number of Participants

As described in Section 16.1 (Determination of Sample Size), two hundred one (201) eligible subjects are planned to be enrolled in the main study while a subgroup of 18-36 (a minimum of 6 and a maximum of 12 subjects per arm) are planned to participate in the PK sub-study.

At the randomization visit (V2), subjects will be 1:1:1 randomized to receiving any of the two daily doses of active treatment or placebo. TID doses of the assigned treatment will be administered from Day 1 to Day 30. On day 30 (V3) just the first daily dose will be administered, and PK assessed (for the PK sub-study only).

Patients will be stratified at randomization based on their L-BT status (negative vs. positive) and PK sub-study participation (yes or not).

Duration of the study:

- overall (including all parts of the study) approximately 14 months from sites activation;
- study period for a single subject: approximately 3 months (time interval for screening, treatment and follow-up).

9.2 Inclusion Criteria

All the following criteria must be met both at the Screening and Randomization visits unless otherwise specified.

- 1. Men and women aged 18 years or older at screening (V1)
- 2. Female participants are eligible if they are:

of non-childbearing potential, i.e.: i) post-menopausal (at least 2 years without spontaneous menses), or ii) surgically sterile (bilateral tubal occlusion, or hysterectomy), or iii) ablation of both ovaries),

or

of childbearing potential with a negative pregnancy test result at screening and randomization and agreeing to use a highly effective method of contraception (i.e. with failure rate of less than 1% per year) until 72 hours after taking the last study treatment dose.

Note 1. Based on Clinical Trial Facilitation Group recommendations, highly effective methods of contraception are the following:

- intrauterine device (IUD);
- intrauterine hormone-releasing systems (IUS) or;
- combined hormonal contraceptives (i.e. estrogen and progestogen) in oral, intravaginal or transdermal form, with inhibition of ovulation as primary mode of action or;
- progestogen-only hormonal contraceptives in oral, injectable or implantable form, with inhibition of ovulation as primary mode of action or;
- absolute and continuous sexual abstinence from Day 1 included (first day of treatment) until 72 hours after taking the last study treatment dose.

Note 2. In each case of delayed menstrual period (over one month between menstruations), female participants of child-bearing potential will be strongly recommended a confirmation of absence of pregnancy. This recommendation applies also to women of child-bearing potential with infrequent or irregular menstrual cycles.
- 3. Presence of rosacea, papulopustular phenotype, defined as papules and/or nodules, with or without pustules of rosacea, without comedones, plus: centrofacial persistent erythema or phyma or transient episodic facial erythema (flushing) or facial telangiectasia (excluding perialar regions) or major ocular rosacea features (i.e. lid margin telangiectasia, interpalpebral conjunctival injection, spade-shaped infiltrates in the cornea, scleritis and sclerokeratitis).
- 4. Presence of \geq 11 and \leq 70 facial papules and/or pustules.
- 5. Moderate (Grade 3) or severe (Grade 4) rosacea based on Investigator's Global Assessment (IGA) based on Investigator's judgement.
- 6. Patients accepting to provide and legally capable of providing free and informed consent to all procedures included in the protocol (including facial skin photography).

9.3 Exclusion Criteria

None of the following criteria must be met both at the Screening visit and at the Randomization visit (Day 1) unless otherwise specified:

- 1. Granulomatous rosacea or rosacea fulminans.
- 2. Erythematoteleangectatic, phymatous or ocular rosacea only. Patients with these subtypes associated with papulopustular rosacea can be enrolled.
- 3. Rosacea with IGA grade ≤ 2 based on Investigator's judgment.
- 4. Anticipated need for proctoscopy or colonoscopy within two weeks after lactulose breath test.

Note 3: Subjects undergoing unanticipated proctoscopy or colonoscopy within two weeks from lactulose breath test should have a thorough bowel cleansing with a non-fermentable solution.

- 5. Subjects requiring a low galactose diet.
- 6. Hypersensitivity or intolerance to lactulose or any excipient of the lactulose preparation to be used for L-BT.
- 7. History of inflammatory bowel disease (Crohn's disease or ulcerative colitis) or other conditions characterized by severe intestinal ulcers.
- 8. History of coeliac disease.
- 9. Patients with intestinal obstruction or partial intestinal obstruction.
- 10. Presence of diarrhoea associated with fever and/or blood in the stool.
- 11. Severe kidney impairment (i.e. estimated glomerular filtration rate <30 ml/min).
- 12. Severe hepatic impairment (i.e. Child-Pugh B or C).
- 13. Cancer or any cancer-related treatment within 5 years prior to screening (excluding nonmelanoma skin-cancer).
- 14. History of alcohol or drug abuse within a year prior to screening, based on Investigator's judgement.
- 15. Facial skin conditions that can interfere with reliable assessment of rosacea throughout the study (e.g. facial hair, tattoos, other facial adornments, keloids, hypertrophic scarring, recent facial surgery, excessive sun exposure including use of tanning beds)
- 16. Any other significant health condition (e.g. cardiovascular, respiratory, renal, hepatic, neurologic, psychiatric, hematologic, oncologic, immune etc.) or non-health condition that in the investigator's judgement may:
 - *iv*) jeopardize the patient's safe participation in the trial or
 - *v*) make unlikely the patient's completion of the study or
 - *vi*) make unlikely the patient's compliance with the study procedures (e.g. highly anticipated need of non-permitted treatments, terminal illness, etc.).

- 17. History of hypersensitivity to rifaximin, rifamycin-derivatives, any of the rifaximin-EIR or placebo excipients.
- 18. Treatment with biologic immunomodulatory and/or immunosuppressive drugs (e.g. anti-TNF drugs) within 6 months prior to randomization.
- 19. Treatment with non-biologic immunomodulatory and/or immunosuppressive drugs (e.g. cyclosporine, methotrexate etc.) within 30 days prior to randomization.
- 20. Treatment with warfarin (or other coumarins) within 14 days prior to randomization.
- 21. Treatment with niacin within 30 days prior to randomization.
- 22. Topical facial or systemic antibiotics within 30 days before randomization;
- 23. Treatment with neomycin or other low-absorbable oral antibiotics (such as marketed rifaximin) within 90 days before randomization.
- 24. Topical facial, inhaled or systemic corticosteroids within 30 days prior to randomization.
- 25. Topical facial retinoids within 30 days before randomization.
- 26. Systemic retinoids within 6 months before randomization.
- 27. Any other topical or systemic treatment for rosacea within 30 days before randomization (including also laser and pulsed light, etc.).
- 28. Over-the-counter intestinal or topical skin probiotics (functional food is allowed), within 30 days before randomization.
- 29. Any experimental treatment within 6 months prior to randomization.
- 30. Current swab-positive or suspected (under investigation) Covid-19 infection; or fever and one or more of the following respiratory disease signs or symptoms: cough, sputum production, shortness of breath within the last 14 days; or contact with people with Covid-19 infection within the last 14 days.
- 31. Women who are pregnant, breast-feeding or planning a pregnancy during the trial period.
- 32. Subjects who are investigational site staff members and their family members, site staff members otherwise supervised by the investigator, or patients who are Alfasigma's employees.

9.4 Premature Discontinuation from the Study per Subject

The subject has the right to withdraw from the study at any time without providing any reason.

Participants may be withdrawn at any time when any of the following conditions occur:

- adverse events; when during the observation period adverse events occur that, in the Investigator's or the patient's opinion, are of such a nature or severity to recommend treatment withdrawal;
- failure to comply with major requirements of the protocol (e.g. inclusion error or evidence of non-compliance with exclusion/inclusion criteria arisen during the study, subject misses study visits or/and is not compliant with key study procedures);
- explicit withdrawn of patient's consent to participate or failure to report to study visits;
- patient's loss to follow-up;
- Investigator's opinion; the Investigator may choose to withdraw a subject from the study if, in the investigator's opinion, continuing the participation in the study for any reason would compromise the safety or well-being of the participant;
- other reasons, different from the ones previously specified.

Reason and date of patient's withdrawal must be recorded in the Patient's Clinical Chart and the e-

CRF.

The study may be terminated prematurely if:

- the Sponsor feel that the number and/or severity of AEs justify discontinuation of the study;
- the Sponsor considers the applied doses of the study drug to be no longer relevant;
- data not known before becoming available and raise concern about the safety of the study drug so that continuation would pose potential risks to the subjects.

Premature termination of the study should be mutually agreed upon by the Coordinating Investigator and the Sponsor and must be documented. However, study results must be reported according to the requirements outlined in this protocol as far as applicable.

The data of subjects who are withdrawn will be considered for evaluation both for efficacy, PK and safety.

Subjects who discontinue treatment due to SAE will be followed up until the event resolves or stabilises.

Subjects withdrawn from the study will not be replaced.

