11.2.8 Early Termination Visit (ETV, from Day 1 to Day 60)

The following procedures will be performed at the ETV visit:

- 1. Concomitant medications recording (change from the previous visit);
- 2. Vital signs recording (heart rate, blood pressure, body temperature);
- 3. Complete physical examination (including also weight and BMI);
- 4. Urine pregnancy tests (women of child-bearing potential only);
- 5. Rosacea-associated facial skin inflammatory lesion count (i.e. papules and pustules);
- 6. Five-points Investigator's Global Assessment (IGA) of Rosacea Severity;
- 7. Other rosacea-associated lesions assessment (i.e. facial erythema, facial telangiectasia, ocular manifestations, phymatous changes);
- 8. Visual analogue scale (VAS);
- 9. Blood collection and performance of the following laboratory tests:
 - haematological tests (haematocrit, haemoglobin, red blood cell count, white blood cell count with differential count, platelet count)
 - clinical chemistry tests (glycaemia, total cholesterol, triglycerides, serum creatinine, urea (or BUN), sodium, potassium, chloride, AST, ALT, Gamma-GT, alkaline phosphatase, total and fractioned bilirubin, erythrocyte sedimentation rate)
 - if not provided by the local laboratory, estimation of glomerular filtration rate
 - C-reactive protein
 - Urinalysis (specific gravity, pH, protein, glucose, ketones, haemoglobin, nitrite [if available], bilirubin, urobilinogen, and microscopic examination [if available]);
- 10. Recording of IBS-SSS and DLQI questionnaires via ePRO;
- 11. Lactulose Breath Test (L-BT): L-BT can be performed either at the study centre under Investigator's supervision or directly by the subject at subject's home. In the latter case, the test has to be performed within 3 days after the ETV visit;
- 12. Adverse Events collection.

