5.4.6 Per Protocol Analysis Set

Per Protocol Analysis (PP) set is defined as all subjects in the FAS who fulfil the study protocol requirements with no major deviations that may affect study results.

Analysis on the PP set will be performed according to the actual treatment received. Patients randomized to a wrong stratification factor level will not be excluded from the PP set and will be analyzed according to the actual stratum (not the randomized one).

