With reference to efficacy analyses performed on the FAS, the last observation carried forward (LOCF) strategy will be employed for dealing with any missing continuous post-baseline data for the relevant primary and secondary endpoints. For binary data (i.e. Success/Failure) missing data will be considered as Failures, unless differently specified in the appropriate analysis section for that data.

With reference to other categorical variables, the number of patients with missing data will be presented under the "unknown" category. Missing values will be included in the denominator count when computing percentages, unless differently specified in the appropriate analysis section for that data.

LOCF imputation will be used for the inferential analysis of categorical variables.

When other continuous data will be summarized, only the non-missing values will be evaluated for computing summary statistics.

Missing data in safety variables will not be imputed/replaced unless otherwise specified in the analysis section.

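### A patient found ineligible after randomisation may be withdrawn from the study, not only from treatment, and nothing then secures the Day 30 co-primary assessment

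*Protocol*

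**What the plan says.** **Withdrawal.** Protocol 9.4 concerns discontinuation from the study. It states: "Participants may be withdrawn at any time when any of the following conditions occur". One condition is failure to comply with major protocol requirements, with the examples "inclusion error or evidence of non-compliance with exclusion/inclusion criteria arisen during the study" and "subject misses study visits or/and is not compliant with key study procedures". The section adds "The data of subjects who are withdrawn will be considered for evaluation both for efficacy, PK and safety" and "Subjects withdrawn from the study will not be replaced". It does not describe a patient who stops tablets but stays under assessment.

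**Visits.** In Protocol 11.1, lesion count and IGA are scheduled at V1, V2 (Day 1), V3 (Day 30 ±1), V4 (Day 60 ±3) and the early termination visit (ETV), and at unscheduled visits if the investigator judges them necessary. Under 11.2.8 the ETV can fall anywhere from Day 1 to Day 60. SAP 5.8 applies no visit windows.

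**Missing data.** In the full analysis set (FAS), SAP 5.9 fills missing continuous endpoints by last observation carried forward (LOCF). It then says "For binary data (i.e. Success/Failure) missing data will be considered as Failures", unless an analysis section specifies otherwise. A later sentence in 5.9 uses LOCF for inferential analysis of categorical variables. SAP 5.4.4 admits a patient to the FAS only with a post-baseline assessment of at least one co-primary endpoint. Protocol 16.2.3 asks only for one dose, although the protocol synopsis has the post-baseline condition.

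**Eligibility errors.** SAP 6.3 counts violations of entry criteria among the deviations to be identified, with evaluability settled before unblinding. SAP 5.4 assigns population decisions to a blind data review. The per-protocol (PP) set is "all subjects in the FAS who fulfil the study protocol requirements with no major deviations that may affect study results".

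**The concern.** An eligibility error found after dosing is a question about which analysis set the patient belongs to, and the plan already answers it through the PP set. Ending the patient's participation does nothing further for the PP set. It does cost the FAS the Day 30 lesion count and IGA, which are the two co-primary measurements.

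At stake are a small number of co-primary outcomes that could have been observed and are replaced by a rule. A patient who would have reached IGA 0 or 1 at Day 30 can be counted as a failure, and a lesion count from, say, the second week can stand in for Day 30. The two planned sensitivity analyses (SAP 7.1) change the treatment label and leave out the first 30 patients. Neither changes the missing-data assumption, and both lack the same observations.

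**Working it through.** **1. The plan's own figure.** Protocol 16.1 starts from 51 per arm and allows about 10% dropout: 51/(1 − 0.10) = 56.7, rounded up to 57, and 3 × 57 = 171. This reproduces the stated 171. The later increase to 67 per arm (201) was for kit misallocation. The 10% covers all causes; no number of eligibility errors is given. The effect, SD, success rates and power are blacked out, so the 51 cannot be checked.

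**2. What happens to a patient withdrawn before Day 30.**

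| Data available after baseline | Lesion count | IGA success |
|---|---|---|
| ETV or unscheduled value | LOCF from that day | Failure, or LOCF under the later sentence of SAP 5.9 |
| None | Outside the SAP FAS; inside the Protocol 16.2.3 FAS | Same |

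No scheduled efficacy visit lies between Day 1 and V3, so no other Day 30 source exists.

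**3. Size per patient.** With 67 per arm, scoring one would-be success as a failure moves that arm's rate by 1/67 = 1.49 percentage points. This is the maximum for one patient so scored.

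**4. Size for several patients (assumed number).** Ten percent of 67 is 6.7 dropouts. If a third to a half followed from section 9.4 eligibility or compliance withdrawals (assumed), that is 2 to 3 per arm. If their true Day 30 success rate is p, the expected shift is (k/67) × p:
- k = 2, p = 0.20: 0.0299 × 0.20 = 0.6 points.
- k = 3, p = 0.40: 0.0448 × 0.40 = 1.8 points.

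**5. Effect on the comparison.** If a share w of each arm is withdrawn and scored as failure, each rate becomes p(1 − w) and the difference shrinks by the factor (1 − w). The illustration below assumes placebo success of 10%, 20% or 30%, with the active rate set so that 51 per arm gives 80% power (32.4%, 45.8% and 57.2%), and an unstratified two-proportion test at two-sided 5%. Power with 67 per arm:

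| w | Scored as failure | Same patients dropped |
|---|---|---|
| 0 | 89.7% | 89.7% |
| 2% | 88.5–88.9% | 89.1% |
| 5% | 86.8–87.6% | 88.1% |
| 10% | 83.5–85.2% | 86.3% |

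Two or three of 67 is w = 3.0% to 4.5%, between the second and third rows.

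**6. Unequal withdrawal with no true effect.** The spurious difference is p × (difference in w). For a 5-point difference and p = 20% to 40%, it is 1.0 to 2.0 points.

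**7. Lesion count under LOCF.** If a fraction f of the effect is present at withdrawal, the estimated effect is multiplied by 1 − w(1 − f). At w = 5% this runs from 0.95 (f = 0) to 0.99 (f = 0.75).

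**The case against.** The case for leaving the text alone has real force.

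- **Missed visits and tablet non-compliance add little.** V3 is the only scheduled clinic visit a patient can miss before the endpoint, so a patient who misses it has already lost the outcome. Tablet compliance is judged from returned bottles (Protocol 10.7) and accountability at V3 or ETV, so it usually comes to light when Day 30 is being assessed. This stands and narrows the point to eligibility errors found between Day 1 and Day 30.
- **Such errors may be few.** Criteria are checked at V1 and confirmed at V2 before randomisation. Withdrawal is permitted, not required.
- **Data are not thrown away.** The ETV records both measures, and withdrawn patients' data are used. This stands, but the value comes from whichever day the patient leaves.
- **Direction of bias.** A reader might infer that poor responders on placebo are withdrawn and that this distorts the comparison. The documents do not support that inference: investigator and patient are blinded, and a poor responder scored as a failure is scored much as Day 30 would have scored them. No direction of bias can be asserted.
- **Larger effect.** A reader might multiply 2 or 3 patients by 1.5 points and report 3 to 4.5 points. That is a ceiling. It needs every withdrawn patient in the arm to be a would-be success, on a count that is itself assumed.

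None of this supplies the missing provision. No text asks a withdrawn, consenting patient to return for V3.

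**Conclusion.** The point holds as a narrow and inexpensive improvement. Protocol 9.4 merges stopping treatment with ending assessments, so an eligibility error found after dosing can cost the Day 30 co-primary values without any gain to the PP analysis. How such a patient then enters the primary analysis is also not uniquely defined: SAP 5.9 contains two rules that could apply to IGA success, and the FAS definitions in SAP 5.4.4 and Protocol 16.2.3 differ.

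The effect cannot be sized from the documents and is probably modest. The range of 0.6 to 1.8 points per arm rests on an assumed 2 to 3 patients, assumed success rates of 20% to 40% and failure scoring; 67 per arm is the planned number, and analysed arm sizes may differ. At 2% to 5% equal withdrawal, the illustrative loss of power is about 1 to 3 points. If errors are few and balanced, the effect is smaller. The documents do not show that the primary comparison is biased, only that it is open to an avoidable loss.

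**What to change.** **Protocol 9.4.** Leave the listed grounds and all treatment-stopping decisions as they are. Because 9.4 is the general discontinuation section, deleting its eligibility grounds could also affect decisions to stop treatment. Add that:

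1. stopping study treatment for any reason, including an eligibility error or non-compliance, does not end assessments;
2. every dosed patient who has not withdrawn consent is asked to attend V3 (Day 30) and V4 (Day 60) for lesion count and IGA;
3. an eligibility error affects only membership of the PP set, decided at the blind review.

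**SAP 5.9.** State one rule for missing IGA success. One way is to limit the LOCF sentence to categorical variables other than the success/failure endpoints. Align the FAS definition with Protocol 16.2.3 at the same time, so that a patient with no post-baseline value is treated in one stated way.

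**Cost.** Amendment wording, a site reminder, and a few visits by patients who are off treatment. V3 and V4 are already scheduled for everyone. A value taken off treatment reflects the patient's state at Day 30, not response to a full course, and some patients will still decline to attend.
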